5. TEST ARTICLE ALLOCATION AND MASKING

5.1. Test Article Allocation

The study lenses will be worn in a bilateral and random fashion using a 2×2 crossover design. A computer-generated randomization scheme will be used to randomly assign subjects, in blocks of 2, to one of the two possible lens wear sequences: Test/Control or Control/Test. The random scheme will be generated using the PROC PLAN procedure from Statistical Analysis System (SAS) Software Version 9.4 or higher (SAS Institute, Cary, NC).

The study site must follow the randomization scheme provided and complete enrollment per the randomization list and not pre-select or assign subjects. The randomized assignment of subjects will be performed at the first visit prior to the first fitting. The following must have occurred prior to randomization:

- Informed consent has been obtained
- Subject meets all the inclusion / exclusion criteria
- Subject history and baseline information has been collected.

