14.5. Primary Analysis

All primary analysis will be conducted on the Per-protocol population.

CLUE Vision

CLUE vision scores at the 2-week follow-up will be analyzed using a linear mixed model adjusting for baseline values as a covariate. Sequence of lens wear, study period, lens type will be included as fixed effects. Other factors such as, race, gender or ADD power may be included in the model as covariates when appropriate. Site will be included as a random effect (G-side). The covariance between residual errors from the same subject across study periods will be modeled using either homogenous compound symmetry (CS) or unstructured (UN). The

Clinical Study Protocol

Johnson & Johnson Vision Care, Inc.

structure that returns the lowest finite-sample corrected Akaike's Information criterion⁷ will be selected as the structure that best fits the model. The Kenward and Roger method, (Kenward and Roger, 1997)⁸ will be used for the denominator degrees of freedom.

Comparisons between the Test and Control lens at the 2-week follow-up evaluation will be carried out using two-sided 95% confidence intervals constructed for the least-square mean difference (Test minus Control).

Primary hypothesis 1:

The null and alternative hypothesis for CLUE vision to test for superiority of the Test lens relative to the pre-defined threshold of 40 is as follows:

$$H_0: \mu_{Test} \leq 40$$
$$H_A: \mu_{Test} > 40$$

Superiority will be declared if the lower limit of the 95% confidence interval of the adjusted mean for the Test lens is greater than 40. i.e. $P(\mu_{Test} > 40) \geq 0.975$.

Primary Hypothesis 2:

The null and alternative hypothesis for CLUE vision to test for non-inferiority of the Test lens relative the Control lens is as follows:

$$H_0: \mu_{Test} - \mu_{Control} \leq -5$$
$$H_A: \mu_{Test} - \mu_{Control} > -5$$

Non-inferiority will be declared if the lower limit of the 95% confidence interval for the least-square mean difference is greater than -5. i.e. $P(\mu_{Test} - \mu_{Control} > -5) \geq 0.975$.

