14.6. Secondary Analysis

Visual Performance (logMAR)

Binocular, high luminance, high contrast visual performance (logMAR) will be analyzed using a linear mixed model. Sequence of lens wear, study period, lens type, distance (4m, 64cm and 40cm) and the lens by distance interaction as fixed effects. Other characteristics including, age, gender and race and ADD power may be included when appropriate. Site will be included as a random effect (G-side). The covariance between residual errors from the same subject and distance across study periods will be modeled using either homogenous compound symmetry (CS) or unstructured (UN) covariance structure. The structure that returns the lowest finite-sample corrected Akaike's Information criterion⁷ will be selected as the structure that best fits the model. The Kenward and Roger method⁸ will be used for the denominator degrees of freedom.

Clinical Study Protocol

Johnson & Johnson Vision Care, Inc.

Comparisons between the Test and Control lenses will be carried out at each distance (4m, 64cm and 40cm) using 2-sided 95% confidence intervals constructed of least square means (LSM) differences (Test minus Control) at the 2-week follow-up evaluation.

Secondary hypothesis 1:

The null and alternative hypothesis for binocular distance HLHC visual performance to test for superiority of the Test lens relative to the pre-defined threshold of 0 logMAR is as follows:

$$H_0: \mu_{Test} \geq 0 \text{ logMAR}$$
$$H_A: \mu_{Test} < 0 \text{ logMAR}$$

Superiority will be declared if the upper limit of the 95% confidence interval of the adjusted mean for the Test lens is below 0 logMAR. i.e. $P(\mu_{Test} < 0) \geq 0.975$.

Secondary hypothesis 2:

The null and alternative hypothesis for binocular near HLHC visual performance to test for superiority of the Test lens relative to the pre-defined threshold of 0.17 logMAR is as follows:

$$H_0: \mu_{Test} \geq 0.17 \text{ logMAR}$$
$$H_A: \mu_{Test} < 0.17 \text{ logMAR}$$

Superiority will be declared if the upper limit of the 95% confidence interval of the adjusted mean for the Test lens is below 0.17 logMAR. i.e. $P(\mu_{Test} < 0.17) \geq 0.975$.

Secondary hypothesis 3:

The null and alternative hypothesis for binocular distance HLHC visual performance to test for superiority of the Test lens relative to the pre-defined threshold of 0.17 logMAR is as follows:

$$H_0: \mu_{Test} \geq 0.17 \text{ logMAR}$$
$$H_A: \mu_{Test} < 0.17 \text{ logMAR}$$

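### The residual covariance is indexed by study period, so the Test-lens intervals compared with fixed thresholds use a variance averaged over both lenses and are mis-sized if the lenses differ in spread

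*Combined protocol and SAP*

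**What the plan says.** Section 14.5 (primary, CLUE vision): "The covariance between residual errors from the same subject across study periods will be modeled using either homogenous compound symmetry (CS"), or else as unstructured (UN), with the structure of lower corrected AIC retained. On the mean model: "Sequence of lens wear, study period, lens type will be included as fixed effects". Baseline CLUE is a covariate and site is a random effect.

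Section 14.6 (secondary, logMAR) has a parallel sentence: "The covariance between residual errors from the same subject and distance across study periods will be modeled using either homogenous compound symmetry (CS) or unstructured". One model covers 4 m, 64 cm and 40 cm.

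Section 5.1 randomizes subjects "in blocks of 2, to one of the two possible lens wear sequences: Test/Control or Control/Test".

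The rule for primary hypothesis 1 concerns the Test lens by itself: "Superiority will be declared if the lower limit of the 95% confidence interval of the adjusted mean for the Test lens is greater than 40". Secondary hypotheses 1-3 have the same form, with the upper limit of the Test mean set against 0 or 0.17 logMAR. Only primary hypothesis 2 (non-inferiority, margin 5) uses the lens difference. Neither section mentions a lens-specific variance, grouping by lens or a robust standard error.

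**The concern.** Four of the five decision rules use the interval for the Test mean, and that interval should reflect how variable scores are on the Test lens. Homogeneous compound symmetry allows one variance. A period-indexed unstructured matrix allows two, but they separate period 1 from period 2. Each period mixes the lenses about equally, so neither structure can isolate the Test variance, and choosing between them by AIC does not help.

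If the Test lens is the more variable of the two, its interval is too narrow and the 2.5% one-sided level built into each rule is exceeded. If it is the less variable, the interval is too wide and power is lost.

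**Working it through.** **Plan figure.** The plan states no precision for the Test mean. Table 5 in Section 14.2 concerns Test minus Control, so it is not a check on this point.

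**Inputs from the documents.** Target of 70 completers (Section 4.3). Control CLUE mean 60.1 and SD 19.58 (Section 14.2). Threshold 40 (Sections 2.3 and 14.5). 1:1 sequences (Section 5.1).

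**Assumed.** SD ratio k = sT/sC, because no Test SD is given. Within-subject correlation 0.6 in the simulations; the formulas for the Test mean do not depend on it.

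**Step 1: the Test mean.** Sequence, period and lens reproduce the four cell means exactly. The least-squares mean for Test is the average of two cells: Test in period 1 (sequence Test/Control) and Test in period 2 (sequence Control/Test). With N/2 subjects per sequence its true variance is

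(1/4)[sT²/(N/2) + sT²/(N/2)] = sT²/N.

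**Step 2: what the model reports.** Each period's variance is pooled over a Test cell and a Control cell, giving (sT² + sC²)/2. Compound symmetry gives the same value. The reported variance is therefore [(sT² + sC²)/2]/N, and

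reported SE / true SE = sqrt((1 + k²)/2) / k.

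One-sided error is approximately 1 − Φ(1.96 × ratio).

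**Step 3: the lens difference.** The within-subject difference has variance sT² + sC² − 2·cov in both sequences. The period-indexed model recovers the same sum, so with complete pairs the non-inferiority standard error is right.

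**Step 4: numbers.** The simulation used N = 70 split 35/35 and 40,000 runs per row.

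| k | SE ratio, formula | error, formula | SE ratio, simulated | error as planned, simulated | error lens-indexed, simulated | non-inferiority error, simulated |
|---|---|---|---|---|---|---|
| 0.8 | 1.132 | 1.3% | 1.132 | 1.32% | 2.53% | 2.38% |
| 1 | 1.000 | 2.5% | 0.993 | 2.56% | 2.56% | 2.46% |
| 1.25 | 0.906 | 3.8% | 0.905 | 3.73% | 2.50% | 2.64% |
| 1.5 | 0.850 | 4.8% | 0.852 | 4.50% | 2.45% | 2.61% |

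Compound symmetry and period-indexed unstructured gave identical results at 35/35. At a 40/30 split with k = 1.5 they gave 4.8% and 4.9%, against 2.5% lens-indexed.

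**Step 5: closer to the planned model.** All at k = 1.5:
- A REML fit with the baseline covariate gave an SE of 2.98 against a true 3.49, and rejection of 5.0% as planned against 2.8% lens-indexed.
- Adding an estimated site effect and the AIC choice (600 runs, so imprecise) gave a mean SE of 3.31 against 3.77 lens-indexed, and rejection of 4.3% against 2.8%. Estimating a site variance widens both intervals and dilutes the error without removing it.
- In runs of that fuller model at SD ratios 0.67, 1 and 1.5, period-indexed unstructured was selected in 14-19% of runs. It did not cure the problem.

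**Step 6: does the CLUE decision move?** Take a Test mean of 60.1 (the Control value), sC = 19.58 and k = 1.5, so sT = 29.37.
- Reported SE: sqrt((29.37² + 19.58²)/2)/sqrt(70) = 2.983. Lower limit: 60.1 − 1.96 × 2.983 = 54.25.
- Correct SE: 29.37/sqrt(70) = 3.510. Lower limit: 60.1 − 1.96 × 3.510 = 53.22.

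Both are far above 40.

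**Step 7: acuity.** Section 1.5 reports means of −0.057 (distance) and 0.091 (near) from an earlier study with 30 completers. Those are 0.057 below 0 and 0.17 − 0.091 = 0.079 below 0.17. No logMAR SD and no intermediate value is given, so these gaps cannot be put in standard-error units.

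**The case against.** **The effect is hypothetical.** It vanishes at equal spread, and nothing in the documents points to unequal spread. CLUE is scaled to a population SD of 20 (Section 2.2), the Control SD is 19.58, and Section 14.2 assumes similar performance. A ratio of 1.5 would need a Test SD of about 29.4. This stands as a limit on size. But similar performance is a power assumption about scores, not a statement about variances, and it does not cover acuity.

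**The study-wide 5% is not shown to be breached.** A reader might infer that the overall error rate in Section 14.4 fails. The documents do not support that. Section 2.3 requires every primary and secondary hypothesis to be met, so the chance of a false overall claim is bounded by the largest component error. By the formula, that error passes 5% only above a ratio of about 1.56. What can be exceeded is the 2.5% level of each rule.

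**The wording could mean lens.** In a two-period crossover, a subject's two periods are also that subject's Test and Control records. Period is much the more natural reading. Under either reading homogeneous compound symmetry still averages the variances and remains a candidate. If lens was intended, saying so settles half the point.

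**Re-indexing alone does not finish the job in 14.6.** Correct. That model shares one covariance across three distances, so a lens-indexed matrix would still pool the Test variance over 4 m, 64 cm and 40 cm. The error rates above were derived for a single endpoint, not for that joint model.

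**Conclusion.** The point holds as a conditional weakness in precision and error rate for the four Test-only rules. As planned, their intervals use an averaged variance. Over an assumed SD ratio of 0.8 to 1.5, the standard error runs from about 13% too large to about 15% too small, and one-sided error from about 1.3% to 4.5-5%, against a nominal 2.5%. At a ratio of 1 nothing is wrong.

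Two stronger conclusions might be drawn, and neither is supported. The non-inferiority result is not in doubt: its interval is unaffected with complete pairs, which the Per-Protocol set in Section 14.3 requires. The CLUE comparison with 40 is not fragile either, since a one-point shift in a lower limit near 54 leaves it intact. Nor can one reassure the reader that the acuity thresholds are comfortably distant, because the documents give no SD from which to say so.

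This is a worthwhile low-cost improvement, not a defect that threatens the trial's main conclusion.

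**What to change.** **Section 14.5.** Specify an unstructured within-subject covariance indexed by lens type (Test, Control), and delete the corrected-AIC choice between compound symmetry and period-indexed unstructured. The new matrix has three parameters, as many as the planned unstructured option. With complete pairs the non-inferiority result is unchanged, and one data-driven model choice disappears. There is no downside of substance.

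**Section 14.6.** Index by lens type and also let the covariance differ by distance, either with a separate lens-indexed unstructured matrix at each distance or with a separate model per distance. Each Test interval then uses the variance at its own distance. The cost is a few more covariance parameters: 3 × 3 = 9, against three for the planned unstructured option. The by-distance lens-difference intervals would also change, because they would no longer pool variance over distances.

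Both are changes to SAP text and model code, and should be made before database lock.

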14.6. Secondary Analysis

Visual Performance (logMAR)

Binocular, high luminance, high contrast visual performance (logMAR) will be analyzed using a linear mixed model. Sequence of lens wear, study period, lens type, distance (4m, 64cm and 40cm) and the lens by distance interaction as fixed effects. Other characteristics including, age, gender and race and ADD power may be included when appropriate. Site will be included as a random effect (G-side). The covariance between residual errors from the same subject and distance across study periods will be modeled using either homogenous compound symmetry (CS) or unstructured (UN) covariance structure. The structure that returns the lowest finite-sample corrected Akaike's Information criterion⁷ will be selected as the structure that best fits the model. The Kenward and Roger method⁸ will be used for the denominator degrees of freedom.

Clinical Study Protocol

Johnson & Johnson Vision Care, Inc.

Comparisons between the Test and Control lenses will be carried out at each distance (4m, 64cm and 40cm) using 2-sided 95% confidence intervals constructed of least square means (LSM) differences (Test minus Control) at the 2-week follow-up evaluation.

Secondary hypothesis 1:

The null and alternative hypothesis for binocular distance HLHC visual performance to test for superiority of the Test lens relative to the pre-defined threshold of 0 logMAR is as follows:

$$H_0: \mu_{Test} \geq 0 \text{ logMAR}$$
$$H_A: \mu_{Test} < 0 \text{ logMAR}$$

Superiority will be declared if the upper limit of the 95% confidence interval of the adjusted mean for the Test lens is below 0 logMAR. i.e. $P(\mu_{Test} < 0) \geq 0.975$.

Secondary hypothesis 2:

The null and alternative hypothesis for binocular near HLHC visual performance to test for superiority of the Test lens relative to the pre-defined threshold of 0.17 logMAR is as follows:

$$H_0: \mu_{Test} \geq 0.17 \text{ logMAR}$$
$$H_A: \mu_{Test} < 0.17 \text{ logMAR}$$

Superiority will be declared if the upper limit of the 95% confidence interval of the adjusted mean for the Test lens is below 0.17 logMAR. i.e. $P(\mu_{Test} < 0.17) \geq 0.975$.

Secondary hypothesis 3:

The null and alternative hypothesis for binocular distance HLHC visual performance to test for superiority of the Test lens relative to the pre-defined threshold of 0.17 logMAR is as follows:

$$H_0: \mu_{Test} \geq 0.17 \text{ logMAR}$$
$$H_A: \mu_{Test} < 0.17 \text{ logMAR}$$

Superiority will be declared if the upper limit of the 95% confidence interval of the adjusted mean for the Test lens is below 0.17 logMAR. i.e. $P(\mu_{Test} < 0.17) \geq 0.975$.

Clinical Study Protocol

Johnson & Johnson Vision Care, Inc.

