2.2. Endpoints

Primary Endpoint:

Overall Quality of Vision

Overall quality of vision will be assessed using the Contact Lens User Experience (CLUE™) questionnaire at the 2-Week follow-up evaluation. CLUE™ is a validated patient-reported outcomes questionnaire to assess patient-experience attributes of soft, disposable contact lenses (comfort, vision, handling, and packaging) in a contact-lens wearing population in the US, ages 18-65. Derived CLUE™ scores using Item Response Theory (IRT) follow a normal distribution with a population average score of 60 (SD 20), where higher scores indicate a more favorable/positive response with a range of 0-120. A 5-point increase in an average CLUE™ score translates into 10% shift in the distribution of scores for population of soft contact lens wearers.⁶

Secondary Endpoint:

Visual Acuity (logMAR)

Multiple assessments of binocular and monocular visual acuity will be made during the study, but the binocular measurements made at the 2-week follow-up evaluation using high contrast letters in bright illuminance conditions will be the primary endpoint. At distance (4 meters), VA is assessed using ETDRS Charts; while near (40 cm) and intermediate (64 cm) assessments will be made using reduced Guillon-Poling charts. Visual acuity will be measured using high and low contrast charts in bright illuminance conditions. Visual acuity will also be measured using high contrast charts in dim illuminance conditions created by the use of goggles.

Other Endpoints:

- CLUE™ Comfort
- CLUE™ Handling
- Lens Optimization Summary
- Mechanical Lens Fit
- Slit Lamp Findings

Clinical Study Protocol

Johnson & Johnson Vision Care, Inc.

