2.3. Hypotheses

All primary and secondary hypotheses must be met in order to satisfy the objective of this study.

Primary Hypotheses

1. After approximately 2 weeks of wear, the mean overall quality of vision score of the Test lens will be statistically better than 40 points on CLUE scale.
2. After approximately 2 weeks of wear, the Test lens will be non-inferior to the Control lens with respect to the overall quality of vision score. A non-inferiority margin of 5 points will be used.

Secondary Hypotheses

1. After approximately 2 weeks of wear, the mean distance visual acuity score of the Test lens will be statistically lower than 0.00 on logMAR scale.
2. After approximately 2 weeks of wear, the mean intermediate visual acuity score of the Test lens will be statistically lower than 0.17 on logMAR scale.
3. After approximately 2 weeks of wear, the mean near visual acuity score of the Test lens will be statistically lower than 0.17 on logMAR scale.

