3.2. Inclusion Criteria

Potential subjects must satisfy all the following criteria to be enrolled in the study:

Inclusion Criteria after Screening:

1. The subject must read, understand, and sign the STATEMENT OF INFORMED CONSENT and receive a fully executed copy of the form.
2. The subject must appear able and willing to adhere to the instructions set forth in this clinical protocol.
3. The subject must be at least 40 years of age and not greater than 70 years of age at the time of consent.
4. Subjects must own a wearable pair of spectacles if required for their distance vision.

Clinical Study Protocol

Johnson & Johnson Vision Care, Inc.

5. The subject must be an adapted soft contact lens wearer in both eyes (i.e. worn lenses a minimum of 2 days per week for at least 6 hours per wear day, for 1 month or more duration).
6. The subject must either already be wearing a presbyopic contact lens correction (e.g., reading spectacles over contact lenses, multifocal or monovision contact lenses, etc.) or, if not respond positively to at least one symptom on the “Presbyopic Symptoms Questionnaire” (Appendix E).

Inclusion Criteria after Baseline:

7. The subject's distance spherical equivalent refraction must be in the range of -1.50 D to -3.75 D in each eye.
8. The subject's refractive cylinder must be ≤ 0.75 D in each eye.
9. The subject's ADD power must be in the range of +0.75 D to +2.50 D.
10. The subject must have distance best corrected visual acuity of 20/20⁻³ or better in each eye.

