1.32	Dispensing Criteria	
The following criteria must be met for lenses to be dispensed and if not all are met subject to be discontinued.
 
 • Distance Snellen acuity equal to or better than 20/30 OU • Subject must indicate that the vision is acceptable. • Subject must indicate that the comfort of the lenses is acceptable. • Lenses must have an acceptable general lens fit. 	
1.33	Patient Instructions	Instruct the Subject the following:	

Clinical Study Protocol
Johnson & Johnson Vision Care, Inc.

		
 • The lenses will be worn on a daily wear basis. • Only enough lenses will be dispensed to the subject to wear for the required number of days until their follow-up visit. No additional lenses will be dispensed. • A new lens will be opened and worn each day. • Instruct the subject to bring back all unworn study lenses. • Instruct the subject no cleaning or disinfecting solutions will be used for this lens type. • If determined necessary by the Investigator sterile non-preserved rewetting drops may be dispensed to be used as needed for dryness. • Subjects will be instructed to wear lenses for a minimum of 6 hours a day, every day during the study. • Subjects will be instructed to wear their glasses when not wearing the study lenses. • A patient instruction booklet will be provided. 
NOTE: In the event a lens is lost or damaged, the subject will return to the clinical site for replacement. As much as reasonably possible, a damaged lens and packaging should be returned to the clinical site (wet, if possible) and then returned to the Sponsor. If lens damage is present, complete the Product Quality Complaint Form. The lens will be stored in labeled vial with saline, and clearly differentiated from the other worn lenses that will be shipped back to the Sponsor.
	
1.34	Schedule Follow-up	The subject will be scheduled to return for their follow-up appointment in 3±1 days.	

Clinical Study Protocol
Johnson & Johnson Vision Care, Inc.

		
NOTE: To count the follow-up visit as a day of wear the Subject must have worn the study lenses for 6 hours prior to the visit.
	
--	--	--	--

VISIT 2

The subjects must present to Visit 2 wearing the study lenses. To be counted as a day of wear the lenses need to have been worn for at least six (6) hours prior to the visit.

Visit 2: Treatment 1 Follow-up 1		
Step	Procedure	Details

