14. STATISTICAL METHODS

14.1. General Considerations

Statistical Analysis will be undertaken by the sponsor or under the authority of the sponsor. A general description of the statistical methods to be implemented in this clinical trial is outlined below.

All data summaries and statistical analyses will be performed using the SAS software Version 9.4 or higher (SAS Institute, Cary, NC). Throughout the analysis of data, the results for each subject/eye will be used when available for summarization and statistical analysis. Unscheduled visits will be summarized separately and will be excluded from the statistical analysis.

Summary tables (descriptive statistics and/or frequency tables) will be provided for all baseline variables, efficacy variables and safety variables as appropriate. Continuous variables will be summarized with descriptive statistics (n, mean, standard deviation [SD], median, minimum and maximum). Frequency count and percentage of subjects or eyes within each category will be provided for categorical data.

Summaries will be presented by study lens type and will be performed separately by completion status (Safety Population, Per-Protocol Population or Intent-to-Treat Population).

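### The joint acuity model in Section 14.6 shares one residual covariance across 4 m, 64 cm and 40 cm, so its per-distance 95% intervals are correctly sized only if acuity SDs are equal

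*Combined protocol and SAP*

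**What the plan says.** Section 14.6 puts the three distances in one linear mixed model: "Sequence of lens wear, study period, lens type, distance (4m, 64cm and 40cm) and the lens by distance interaction as fixed effects". Site is the only random effect. On the residuals it says: "The covariance between residual errors from the same subject and distance across study periods will be modeled using either homogenous compound symmetry (CS"; the sentence goes on to offer UN, and AICc picks between those two only.

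Two sets of intervals come from this model. The acuity hypotheses in Section 2.3 compare a Test-lens mean with a fixed threshold. The first is that "the mean distance visual acuity score of the Test lens will be statistically lower than 0.00 on logMAR scale"; intermediate and near use 0.17. Each is decided on the upper 95% limit of the Test mean. Separately: "Comparisons between the Test and Control lenses will be carried out at each distance (4m, 64cm and 40cm) using 2-sided 95% confidence intervals". No hypothesis rests on that second set.

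No acuity SD appears anywhere in the documents.

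**The concern.** The residual block is one subject at one distance, seen in two periods: a 2×2 matrix. CS gives it one variance and one correlation. UN lets the variance differ by period. Neither is indexed by distance, so the AICc step has no candidate in which 4 m, 64 cm and 40 cm have different variances. With complete data the three Test means share one standard error, and so do the three Test-minus-Control differences.

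If the true SDs differ, the interval is too wide where acuity is least variable and too narrow where it is noisiest. A too-narrow interval raises the false-success rate of that threshold test and overstates the precision of the lens comparison. A too-wide one costs power, and Section 2.3 requires every primary and secondary hypothesis to be met.

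**Working it through.** **Inputs from the documents.** 70 completers (Section 4.3); the model (14.6); thresholds 0.00, 0.17 and 0.17 (2.3); earlier Test-lens means of −0.057 at distance and 0.091 at near (1.5). The plan states no acuity SD, power or interval width, so there is no figure to reproduce; Table 5 covers CLUE only.

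**Assumed.** The SDs; 7 sites of 10; between-period correlation 0.6; site SD 0 to 0.04; correlation between distances 0 to 0.5.

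**Step 1, shared standard error.** Direct REML fits of the model to two simulated datasets gave Test-mean standard errors of 0.01347 and 0.01699, each identical at all three distances.

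**Step 2, Test-minus-Control intervals.** In a balanced crossover the true variance of the difference at distance d is 2σ_d²(1−ρ)/n. The joint model replaces σ_d² by the mean of the three variances. The width ratio is r_d = √(mean σ²)/σ_d, and coverage is 2Φ(1.96 r_d) − 1.

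| SDs | √(mean σ²) | r_d | Coverage |
|---|---|---|---|
| equal | σ | 1/1/1 | 95% each |
| 0.08/0.10/0.10 | √0.00880 = 0.0938 | 1.17/0.94/0.94 | 97.8/93.4/93.4% |
| 0.08/0.10/0.12 | √0.01027 = 0.1013 | 1.27/1.01/0.84 | 98.7/95.3/90.2% |

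Simulation agrees: about 97/93/93% for the first unequal set, and 98.5-98.8/95.1-95.5/89.8-90.4% for the second. In a simulation that included the AICc step, UN was chosen in about a quarter of unequal-SD trials and did not repair coverage.

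**Step 3, threshold tests.** These depend on the site term too. The model treats a subject's three distances as independent. Positive correlation between them inflates the estimated site variance and widens these intervals at every distance, which partly offsets the inflation. With equal SDs and correlation 0.3-0.5 this effect alone makes the standard error 2-12% too large and the error 1.4-2.4%.

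One-sided error at the noisiest distance (nominal 2.5%), random site fitted:

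| SDs | Correlation 0.3-0.5 | Correlation 0 |
|---|---|---|
| 0.08/0.10/0.10 | 1.8-2.8% | 2.7-3.1% |
| 0.09/0.10/0.11 | 2.1-2.8% | 3.1-3.3% |
| 0.08/0.10/0.12 | 3.0-3.6% | 3.7-4.4% |

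With no site term at all, 0.08/0.10/0.12 gives 1 − Φ(1.96 × 0.844) = 4.9%; an 800-run simulation gave 5.5%, with simulation error of about 0.8 points. With 5 sites of 14 or 10 of 7, the error for 0.08/0.10/0.12 was 2.7-4.4% over correlations 0 to 0.5.

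**Step 4, power.** Take SDs 0.08/0.10/0.12 and a true mean 0.03 inside its threshold. At the least variable distance, power is 61-65% jointly against 79% with separate models (site SD 0), and 27% against 30-31% (site SD 0.04).

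**Step 5, decisions at the earlier means.** Headroom is 0.00 − (−0.057) = 0.057 at distance and 0.17 − 0.091 = 0.079 at near. Without a site effect, power is at least 0.999 with either variance treatment for SDs up to about 0.13. With random site and correlation 0.3-0.5, joint and separate models disagreed as follows (ranges run over site SD 0 to 0.04):

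- Distance, 4 m least variable: 0.1-7.5% of trials, against 1.0-8.2% with equal SDs, so no increase.
- Near, 40 cm noisiest: 0.2-4.8%, against 0-3.0%.
- Distance, if 4 m were the noisiest: 4.2-10.4%, about 2 to 4 points above equal SDs.

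**Step 6, the remedy.** Distance-specific residual variances in the same joint model restored coverage to about 94-96% and cost about 1 point of power when SDs were equal.

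**The case against.** The premise is not in the documents, and the indirect support for it is thin.

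- **Charts.** Section 2.2 says "VA is assessed using ETDRS Charts; while near (40 cm) and intermediate (64 cm) assessments will be made using reduced Guillon-Poling charts". Only 4 m stands apart, which suggests at most one differing SD, not a three-step ladder. For that pattern (0.08/0.10/0.10) the threshold error is close to nominal.
- **Acuity floors.** Section 3.2 has a floor ("The subject must have distance best corrected visual acuity of" 20/20⁻³ or better), but it is best-corrected acuity, not acuity in the study lens. The dispensing floor in Section 7.2, "Distance Snellen acuity equal to or better than 20/30 OU", is about 0.18 logMAR. Truncating there around a mean of −0.057 trims an assumed SD of 0.10 by only about 3%. Near vision is screened too, through the subject's acceptance of vision and the modification step.
- **Headroom.** At the earlier means the decisions hardly move, and the largest miscoverage is in intervals that carry no hypothesis.

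These points stand and set the size of the concern.

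It can also be said that Section 14 is only "A general description of the statistical methods to be implemented in this clinical trial", and that Section 14.10 allows documented changes. That does not remove the point. The text names the block and both candidate structures. A 6×6 covariance over distance and period is not what it describes, because residuals at different distances fall in different blocks. Section 14.10 covers reporting a change, not specifying the variance beforehand.

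A reader might infer that the acuity tests have a demonstrated error inflation, or that the different charts prove unequal variances. The documents support neither: with equal SDs there is no material problem, and the mild scenarios are essentially nominal.

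**Conclusion.** The concern holds as a conditional, low-severity point. As written, the per-distance 95% intervals are correctly sized only under equal acuity SDs, an assumption the plan neither states nor supports with data. For SDs of 0.08/0.10/0.10 to 0.08/0.10/0.12, lens-difference coverage is about 97-99% at the least variable distance and 90-93% at the noisiest. The harm there is misreported precision. Threshold error at the noisiest distance is about 2-3% under the mild spreads. For the wider spread it is 3.0-3.6% with correlation between distances, and about 4-5% without correlation or with site left out of the model.

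All of these sizes rest on assumed SDs, site structure and correlations. Error inflation matters only if a true mean sits at its threshold; lost power matters only if one lies close inside it. At the Section 1.5 means neither applies to distance or near. No earlier mean is given for 64 cm, so headroom there is unknown.

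**What to change.** Keep the joint model and state that the residual covariance may differ by distance. For example, put GROUP=distance on the CS or UN period block and let AICc choose between the two grouped structures. Or specify a subject-level period-by-distance block, which would also carry the correlation between distances that the grouped version leaves out.

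The cost is SAP wording and the model statement; no new data are needed. Grouping takes CS from 2 to 2 × 3 = 6 covariance parameters and UN from 3 to 3 × 3 = 9; a fully unstructured 6×6 block needs 6 × 7/2 = 21. The power cost is about 1 point if the SDs are equal.

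Separate models per distance are a fallback. No planned hypothesis compares distances, so no test would be lost. But when acuities are equally variable and uncorrelated, separate models can lose about 9 points of power (68% to 59% at 0.03 inside the threshold, site SD 0).
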